7.4.4 Subgroup Analyses

In order to provide additional characterization and interpretation of the primary effectiveness and safety outcomes, the following subgroup analyses may be performed at the time of early success and final analysis in the mITT and PP analysis sets for the primary safety and effectiveness endpoints, respectively. Descriptive statistics will be presented for the primary safety and effectiveness outcomes in each subgroup. No inferential statistical analysis will be performed to test for differences between subgroups. Confidence intervals may be constructed for clinical relevance only. Descriptive statistics will consist of the number and rate of primary adverse events for the primary safety endpoint and Kaplan-Meier plots and estimates for the primary effectiveness endpoint in each subgroup.

- **Baseline Characteristics:**
 - Age group: <65 vs. ≥65 years
 - Sex
 - CHA₂DS₂-VASC Score: ≤2 vs. >2

7.4.5 Exploratory Analysis

Univariate and multivariate logistic regression analyses will be performed to examine the impact of demographic, baseline, and relevant procedural characteristics (e.g., age, sex, LA size, AF duration, medical history, number of PFA applications, etc.) on the primary outcomes. The outcome variables (i.e., primary effectiveness and safety outcomes) will be the dependent variables and baseline, demographic, and procedural characteristics will be treated as independent variables. Univariate logistic regression models will be conducted for each of the potential predictors. A p-value < 0.20 will be used as the cut-off for screening covariates. A multivariable model will be fit including the selected covariates from the univariate models. A final parsimonious multivariable model will be constructed by taking into consideration multicollinearity and clinical relevance of variables that retain a p-value < 0.20 when modelled jointly. The identification of relevant associations with baseline factors provides additional characterization and interpretation of the primary effectiveness and safety outcomes.

7.4.6 Site Heterogeneity

Descriptive summaries of the primary safety and effectiveness endpoints will be provided by site. The PAE and primary effectiveness success rates will be presented by sites in the mITT and PP analysis sets, respectively. This analysis will be performed at the final analysis when all subjects complete their 12-month follow-up. If early success is declared, PAE estimates by site will be presented for the primary safety endpoint. As follow-up will be ongoing at the time of early success if declared, no site level estimates will be presented for the primary effectiveness endpoint.

7.5 Analysis of Secondary Endpoints

No formal statistical hypothesis or inferential statistics will be formulated or performed for the secondary endpoints. Descriptive statistics will be provided on all secondary endpoints in the mITT and PP analysis sets, unless otherwise specified. Acute procedural success rates and Kaplan-Meier estimates and plots for freedom from documented symptomatic recurrence will be presented at the time of early success interim analysis with available data. All secondary endpoints will be analyzed at the time of final analysis using full 12-month follow-up data.

7.5.1 Acute Procedural Success

Acute procedural success is defined as confirmation of entrance block in all clinically relevant targeted PVs after adenosine/isoproterenol challenge. Use of a non-study catheter for PVI and

failure to have PFA delivery with the study catheter due to IRE system malfunctions are considered acute procedural failures.

The rate of acute procedural success will be summarized descriptively. The number and percentage of subjects with acute procedural success will be presented.

7.5.2 Freedom from Documented Symptomatic Recurrence

The symptomatic recurrence endpoint is defined as freedom from documented symptomatic atrial arrhythmia (AF, AT or AFL) recurrence based on electrocardiographic data (≥ 30 seconds on arrhythmia monitoring device) during the effectiveness evaluation period (Day 91-Day 365). Acute procedural failure (i.e., failure to confirm entrance block in all PVs except those that are silent and/or cannot be cannulated post-procedure, use of non-study catheter for PVI, and failure to have PFA delivery with the study catheter due to IRE system malfunctions) will also be considered a failure. Subjects without effectiveness failure who undergo a repeat ablation procedure during the blanking period where PVs were ablated with a commercially available catheter and generator will be considered non-assessable for long-term effectiveness of the IRE ablation system and thus will be excluded from this analysis.

Symptomatic recurrence will be summarized descriptively as the number and percent of subjects event-free during the evaluation period. Kaplan-Meier estimates and plots will be used to characterize the time to first documented symptomatic AF, AT or AFL recurrence following the initial ablation procedure. The probability of freedom from symptomatic AF, AT or AFL recurrence at each follow-up timepoint post blanking will be presented.

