### 8.2.1 Primary Endpoints

- **Acute Safety**

The primary safety endpoint is the incidence of PAEs (within seven (7) days of the initial mapping and ablation procedure). PAEs include the following AEs:

Atrio-Esophageal Fistula*	Phrenic Nerve Paralysis (permanent)
Cardiac Tamponade/perforation	Pulmonary Vein Stenosis*
Device or procedure related death*	Stroke/CVA
Major Vascular Access Complication/Bleeding	Thromboembolism
Myocardial Infarction	Transient Ischemic Attack (TIA)
Pericarditis	

\* Device or procedure related death, pulmonary vein stenosis and atrio-esophageal fistula that occur greater than one week (7 days) post-procedure are considered and analyzed as PAEs.

A 14% performance goal is set for the primary safety endpoint

- **Long term effectiveness:**

Freedom from documented (symptomatic and asymptomatic) atrial arrhythmia (AF, AT or AFL) episodes based on electrocardiographic data ( $\geq 30$  seconds on arrhythmia monitoring device) during the effectiveness evaluation period (Day 91-Day 365). Acute procedural failure (i.e., failure to confirm entrance block, with or without touch-up, in all PVs except those that are silent and/or cannot be cannulated post-procedure) will be considered a long-term effectiveness failure.

A 50% performance goal is set for the primary long-term effectiveness endpoint

Further refer to appendix 1 for definitions on long term effectiveness terms.

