### 8.2.2 Secondary Endpoints

- Acute Procedural Success defined as confirmation of entrance block in all clinically relevant targeted PVs after adenosine/isoproterenol challenge. Use of a non-study catheter to achieve PVI is considered an acute procedural success failure.
- Freedom from documented symptomatic atrial arrhythmia (AF, AT or AFL) episodes based on electrocardiographic data ( $\geq 30$  seconds on arrhythmia monitoring device) during the effectiveness evaluation period (Day 91-Day 365).
- Quality of Life: the change of QoL assessed by comparing the Atrial Fibrillation Effect on Quality-of-Life (AFEQT™) scores before and after the ablation procedure. Note: Patient questionnaires will only be used in countries with validated languages.

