### 20.4.5 Secondary Endpoint Analysis

All secondary endpoints will be summarized based on the full 12-month follow-up data of subjects in the mITT-Wave II analysis sets.

**Acute Procedural Success:** The rate of acute procedural success (defined in section 8.2.2) will be summarized descriptively.

**Freedom from Documented Symptomatic Recurrence:** The rate of freedom from documented symptomatic atrial arrhythmia (atrial fibrillation (AF), atrial tachycardia (AT) or atrial flutter (AFL)) episodes will be summarized descriptively.

**Quality of Life (QOL):** AFEQT scores assessed at baseline and follow-up visits will be summarized and compared descriptively.

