Kaplan-Meier estimates and plots will be used to characterize the time to first primary effectiveness event, including acute procedural failure and documented symptomatic/asymptomatic AF, AT or AFL recurrence following the initial ablation procedure. This will provide a non-parametric estimate of the primary effectiveness endpoint. The Kaplan-Meier analysis will account for all follow-up time for all subjects in the analysis set. Subjects with incomplete follow-up who remain failure free will be censored at the time of last observation. The probability of freedom from primary effectiveness failure at each monthly timepoint post blanking will be presented along with the one-sided 99.75% lower confidence bound using Greenwood's variance.

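### SAP 7.5.2 counts acute procedural failure as a failure of freedom from symptomatic recurrence, which the protocol defines by recurrence alone, and the change is not declared

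*SAP*

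**What the plan says.** Protocol 8.2.2 names the secondary endpoint as "Freedom from documented symptomatic atrial arrhythmia (AF, AT or AFL) episodes based on electrocardiographic data", with a 30-second minimum, during Day 91 to Day 365. Protocol 20.4.5 plans a descriptive summary in mITT-Wave II of "The rate of freedom from documented symptomatic atrial arrhythmia". Neither place mentions acute procedural failure. The protocol attaches that component to the primary effectiveness endpoint in 8.2.1, where acute procedural failure "will be considered a long-term effectiveness failure".

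SAP (Wave II) 7.5.2 opens with the same recurrence definition and then adds acute procedural failure. Its list covers entrance block that was not confirmed and PV isolation that relied on any catheter other than the study one; the last item reads "failure to have PFA delivery with the study catheter due to IRE system malfunctions) will also be considered a failure". Two summaries follow. One is a percentage: "Symptomatic recurrence will be summarized descriptively as the number and percent of subjects event-free during the evaluation period". The other is a Kaplan-Meier analysis to "characterize the time to first documented symptomatic AF, AT or AFL recurrence following the initial ablation procedure".

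SAP (Wave I) 7.5.2 has the same added component but describes only a Kaplan-Meier analysis. For the AF-only additional endpoint, Protocol 8.2.3 again gives recurrence alone, while 7.6.3 in both SAPs adds acute procedural failure.

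**The concern.** One named endpoint has two definitions. The rate that the SAP would report as freedom from symptomatic recurrence mixes recurrence with procedural outcome, so it is not the quantity that the protocol named.

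The added group is also wider than unconfirmed entrance block, which is all that Protocol 8.2.1 lists as acute failure for the primary endpoint. Subjects whose veins were isolated with help from a non-study catheter become failures whatever their rhythm afterwards. They can enter both sets used for secondary endpoints in the Wave II SAP, because its per-protocol criteria in 5.1 do not list non-study catheter use as an exclusion (Protocol 20.3.2 did).

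Within Wave II 7.5.2, the Kaplan-Meier sentence does not repeat the acute-failure component. Two programmers could build the curve with different events. No time is given for placing a failure that occurs on the day of the procedure.

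**Working it through.** **1. The texts side by side**

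| Place | Symptomatic recurrence, Day 91–365 | Acute procedural failure |
|---|---|---|
| Protocol 8.2.2, 20.4.5 | counts | not mentioned |
| SAP Wave II 7.5.2, endpoint definition | counts | counts |
| SAP Wave II 7.5.2, percentage sentence | counts | not repeated |
| SAP Wave II 7.5.2, Kaplan-Meier sentence | counts | not repeated |
| SAP Wave I 7.5.2, endpoint definition | counts | counts |

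The first two rows conflict. Wave II 7.5.2 does not mention a change from the protocol. The Wave I history of changes records a clarification of how acute failure is derived, but does not say that the symptomatic endpoint departs from the protocol.

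**2. Size of the shift**

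The documents give no assumed rate for this endpoint, so there is no planned figure to reproduce. Let a be the share with acute procedural failure, S the symptomatic-recurrence-free proportion among the others, and Sa the same proportion among subjects with acute failure.

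- Protocol definition: (1 − a) × S + a × Sa
- SAP definition: (1 − a) × S
- Difference: a × Sa

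All values below are assumptions: S from 65% to 85%, Sa from 50% up to S.

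| a | Difference, Sa = 50% | Difference, Sa = 85% |
|---|---|---|
| 0% | 0 points | 0 points |
| 1% | 0.5 | 0.85 |
| 5% | 2.5 | 4.25 |
| 10% | 5.0 | 8.5 |

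Example with a = 5% and S = Sa = 75%: the protocol rate is 0.95 × 0.75 + 0.05 × 0.75 = 75.0%, the SAP rate is 0.95 × 0.75 = 71.25%, and the difference is 3.75 points.

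The formula takes every acute failure to be assessable for recurrence. Subjects with no energy delivered are followed for only 3 months (Protocol 10.3, SAP Wave II 7.2). If they are left out of the recurrence-only rate as missing, that rate is S and the difference is S − (1 − a) × S = a × S, the upper end of the range for that S.

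**3. Does the Wave II SAP use different events for the percentage and the curve?**

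The primary-endpoint Kaplan-Meier analysis in Wave II 7.4.2.1 is to "time to first primary effectiveness event, including acute procedural failure and documented symptomatic/asymptomatic AF, AT or AFL recurrence", so there the component is written into the event. In 7.5.2 it is not. But the acute-failure sentence in 7.5.2 comes before both summaries and defines the endpoint for the whole section. Elsewhere the plans use recurrence-only Kaplan-Meier wording while plainly counting acute failure. Wave I 7.5.2 and the AF-only endpoint in Wave I 7.6.3 describe nothing but a Kaplan-Meier analysis, so their acute-failure sentences would otherwise have no effect. In Wave II 7.6.3 the AF-only acute-failure sentence stands between the Kaplan-Meier sentence and the reported probability and percentage. The wording is therefore ambiguous; it does not assign one event to the percentage and another to the curve.

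**4. Would a gap between percentage and curve prove different events?**

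No. With the SAP Appendix I Table 2 hazards for 65% (0.1397, 0.0063, 0.0037 per week), exp(−[2 × 0.1397 + 6 × 0.0063 + 31 × 0.0037]) = exp(−0.4319) = 0.649, which matches the table. These are primary-endpoint hazards, used here only as an illustration. A simulation with them, one event definition, 15% dropout per year and failure-free dropouts excluded from the percentage gave 62.5% for completers against 64.9% for the Kaplan-Meier target. Dropout alone can separate the two summaries by about 2.4 points.

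**The case against.** The strongest defence is that counting acute failure in every long-term effectiveness endpoint is a coherent rule, applied alike to the primary, symptomatic and AF-only endpoints. It can only lower the reported success rate, so it does not flatter the device. Acute procedural success is reported separately in 7.5.1, so readers can see how many acute failures there were. The endpoint is descriptive and carries no hypothesis (Wave II 7.5). Protocol 20 leaves analysis detail to the SAP, and the protocol's mITT definition already calls discontinuation for study-catheter reasons an acute effectiveness failure.

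Most of this stands and limits the consequence. It does not remove the mismatch. The mITT wording concerns acute effectiveness and does not extend to symptomatic freedom. A SAP may detail an analysis, but changing what counts as an event in a protocol endpoint should be declared.

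Two stronger readings are tempting. A reader might infer that Wave II 7.5.2 necessarily yields two different rates, a composite percentage and a recurrence-only curve. The documents do not support this: the composite sentence governs the whole section, and the same curve wording is used elsewhere with acute failure counted. A reader might also infer that the early-success figure cannot be compared with the final one. Wave II 7.5 shows the Kaplan-Meier estimate at the early look and analyses all secondary endpoints again at the end, so curve can be compared with curve.

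**Conclusion.** The protocol and both SAPs define freedom from symptomatic recurrence differently, and the SAPs do not declare it. The AF-only additional endpoint has the same difference. This is settled by the texts and rests on no assumption.

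The size does rest on assumptions. The shift is a × Sa: zero if there are no acute failures, and 2.5 to 4.25 points at an assumed a of 5% with Sa between 50% and 85%. It needs at least one subject with an acute failure who is not also a recurrence failure. Setting the shift against a standard error adds little, because both rates come from the same subjects and no test is planned.

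The Kaplan-Meier wording in Wave II 7.5.2 is a secondary point: an ambiguity to close, not an established split. No primary decision, error rate or sample size is touched. The correction is still worth making, because it changes a reported result and uses data already collected.

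**What to change.** In SAP 7.5.2 (Wave I and Wave II), and for the AF-only endpoint in 7.6.3 of both plans:

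- Report the protocol-defined, recurrence-only endpoint, with one stated event definition for the percentage (where one is reported) and the Kaplan-Meier estimate.
- Add a labelled supplementary row and Kaplan-Meier curve that also count acute procedural failure, placed as an event at time 0.
- If the SAP keeps the composite in any main table, say that it departs from Protocol 8.2.2 or 8.2.3 and give the reason.

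The cost is SAP wording plus one extra row and one extra curve per endpoint. No new data are needed.

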7.5.3 Quality of Life (QOL)

The Atrial Fibrillation Effect on Quality-of-Life (AFEQT™) includes 20 questions on a 7-point Likert scale. Questions 1-18 evaluate Health Related Quality of Life (HRQoL) and questions 19-20 relate to patients' satisfaction with treatment. The first 18 questions are used to calculate the Overall AFEQT score and the subscale scores across three domains as follows:

- AF related Symptoms: Four questions (1 – 4)
- Daily Activities: Eight questions (5 – 12)
- Treatment Concerns: Six questions (13 – 18)

The formula to calculate these scores is as follows:

$$100 - \left[\frac{(\text{sum of severity for all questions answered} - \text{number of questions answered}) \times 100}{\text{total number questions answered} \times 6} \right]$$

Overall and subscale scores range from 0 to 100. A score of 0 corresponds to complete disability, while a score of 100 corresponds to no disability.

Baseline AFEQT scores and changes from baseline at each timepoint the questionnaire is administered will be summarized descriptively for the following five scores. The overall AFEQT score and subscale scores across study visits will also be plotted.

- Overall AFEQT Score (18 questions)
 - Symptom Subscale Score (4 questions)
 - Daily Activities Subscale Score (8 questions)
 - Treatment Concern Subscale Score (6 questions)
- Treatment Satisfaction Score (2 questions)

The AFEQT questionnaire will only be used in countries with validated languages. These analyses will be conducted for subjects in countries where the AFEQT questionnaires are applied.

7.6 Analysis of Additional Endpoints

No formal statistical hypothesis or inferential statistics will be formulated or performed for the additional endpoints. Descriptive statistics will be provided on all additional endpoints in the analysis sets specified below. Procedural data, additional safety endpoints, and additional effectiveness endpoints using Kaplan-Meier estimates and plots where relevant will be presented at the time of early success interim analysis with available data. All additional endpoints will be analyzed at the time of final analysis using full 12-month follow-up data.

7.6.1 Procedural data

Procedural data such as total procedure time, mapping time, PFA application time, number of PFA applications by PV and by subject, total fluoroscopy time, study catheter dwell time, ablation settings used, and use of anesthesia will be summarized descriptively for subjects in the PP analysis set.

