### 8.2.3 Additional Endpoints

- **Safety**
  - Occurrence of individual PAEs from the primary composite
  - Occurrence of Serious Adverse Device Effects (SADEs)
  - Occurrence of Serious Adverse Events (SAEs) within 7 days (early-onset), 8-30 days (peri-procedural) and  $>30$  days (late onset) of initial ablation procedure
  - Occurrence of non-SAEs
  - Occurrence of clinically symptomatic severe PV stenosis as documented by CT/MRA
- **Effectiveness**
  - Ablation by a non-study catheter for PVI (touch-up) among all clinically relevant targeted PVs and by subject
  - Acute reconnection identified by adenosine/isoproterenol challenge.
  - % repeat ablation within the 12M FU period
    - Timing (blanking period or after blanking)
    - % PV reconnection
  - Freedom from documented (symptomatic and asymptomatic) atrial fibrillation (AF) episodes based on electrocardiographic data ( $>30$  seconds on arrhythmia monitoring device) during the effectiveness evaluation period (Day 91-Day 365).
  - Freedom from documented (symptomatic and asymptomatic) atrial arrhythmia (AF, AT or AFL) episodes based on electrocardiographic data ( $\geq 30$  seconds on arrhythmia monitoring device) during the effectiveness evaluation period (Day 91-Day 365) with the following criteria also deemed failure (Appendix 1):
    - Taking a new class I/III AAD for AF or a previously failed class I/III AAD at a greater than the highest ineffective historical dose for AF during the effectiveness evaluation period
    - Greater than 2 repeat ablations for AF/AT/AFL in the blanking period or any repeat ablation for AF/AT/AFL during the effectiveness evaluation period
- **Procedural data, including but not limited to**
  - Total procedure time
  - Mapping time

- PFA application time
  - Number of PFA applications by PV and by subject
  - Total fluoroscopy time
  - Study catheter dwell time
  - Ablation settings used
  - Use of paralytics and anesthesia
- **Neurological Assessment (Wave I)**
    - Occurrence of new post-ablation asymptomatic and symptomatic cerebral emboli as determined by MRI evaluations
    - Occurrence of new or worsening neurological deficits post-ablation and at follow-up, compared to baseline
    - Occurrence, anatomical location and size of asymptomatic and symptomatic cerebral emboli observed pre-and post-ablation as determined by MRI evaluations.

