**Other procedural parameters are collected via Electronic Data Capture (EDC), including but not limited to:**

- Use of a non-study catheter for PVI
- Number of PFA applications per target PV
- Number of RF applications required with a non study catheter
- PVI confirmed with Lasso® or PentaRay or Circular IRE Catheter
- PV acute reconnection (early or dormant)
- Procedure time (from first femoral puncture to last catheter out)
- Mapping time (start mapping - end mapping)
- Total fluoroscopy time
- Total study catheter LA dwell time (from first study catheter insertion in LA until study catheter removal from LA)
- ECG data
- Total fluid delivered via study catheter
- Total fluid delivered via intravenous line (if captured)
- Fluid output (if captured)
- Device deficiency information (if applicable)
- Procedural medication (paralytics)
- Anesthesia type

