### 20.4.6 Additional Endpoint Analyses

No formal statistical hypothesis and inferential statistics will be formulated and performed for the additional endpoints. Additional safety endpoints will be analyzed in Roll-in, Safety and mITT analysis sets for respectively Wave I and Wave II. Effectiveness endpoints and procedural data will be analyzed in FAS and PP analysis sets for respectively Wave I and Wave II. NAE, CT/MRA, and esophageal lesion endpoints will be analyzed in the mITT-Wave I analysis set. All endpoints will be analyzed for the roll-in analysis set separately. Details of the analyses will be described in the SAP.

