7.6.1 Procedural data

Procedural data such as total procedure time, mapping time, PFA application time, number of PFA applications by PV and by subject, total fluoroscopy time, study catheter dwell time, ablation settings used, and use of paralytics and anesthesia will be summarized descriptively. These analyses will be conducted separately in the FAS and PP analysis sets.

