7.6.3 Additional Effectiveness Endpoints

The following analyses for the additional effectiveness endpoints will be conducted in the mITT and PP analysis sets unless otherwise specified and summarized descriptively:

- **Ablation by non-study catheter for PV isolation:** The number and percentage of subjects and number and percent of clinically relevant targeted PVs ablated by a non-study catheter (NSC) for PVI will be summarized.

- Rate of ablation by NSC for PVI among all clinically relevant targeted pulmonary veins:

$$= \frac{\text{Number of PVs ablated by NSC}}{\text{Number of ablated PVs}}$$

- Rate of ablation by NSC for PVI among subjects:

$$= \frac{\text{Number of subjects with at least one PV ablated by NSC}}{\text{Total number of subjects ablated for PVI}}$$

- **Acute PV reconnection:** The number and percentage of subjects and number and percentage of targeted PVs where acute reconnection was identified by adenosine/isoproterenol challenge.

- Rate of acute PV reconnection among targeted veins:

$$= \frac{\text{Number of PVs with reconnection after adenosine/isoproterenol challenge}}{\text{Total number of PVs undergoing adenosine/isoproterenol challenge}}$$

- Rate of acute PV reconnection among subjects:

$$= \frac{\text{Number of subjects with PV reconnection in at least one PV after adenosine/isoproterenol challenge}}{\text{Total number of subjects undergoing adenosine/isoproterenol challenge in all targeted PVs}}$$

- **Repeat ablation during the 12-month follow-up period**

- **Occurrence of repeat procedures:** Kaplan-Meier estimates and plots will be used to characterize the time to the first repeat ablation procedure for study related arrhythmia. The probability of freedom from repeat ablation for study related arrhythmia at each follow-up timepoint post index procedure will be presented. Additionally, the total number of repeat procedures, number of subjects undergoing a repeat procedure, and percentage of subjects undergoing a repeat procedure will be presented by type of arrhythmia treated (overall (all

arrhythmias), AF and AFL or AT (left atrium)), and by timing of the repeat procedure (during the blanking period (Day 1-90) and during the evaluation period (Day 91-365)).

- **PV reconnection:** The number and percentage of subjects and number and percentage of targeted PVs at the repeat procedure where PV reconnection was observed

- Rate of PV reconnection among previously isolated veins:

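### Wave II procedural data are summarised in the Per Protocol set alone, and paralytic use, a listed and collected endpoint, is not named

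*SAP*

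**What the plan says.** The Wave II SAP (7.6.1) gives a list of procedural items, the last of which is anesthesia without paralytics, and states that they "will be summarized descriptively for subjects in the PP analysis set". No other set is named for these items in the main phase. For the additional effectiveness endpoints, 7.6.3 says that the analyses "will be conducted in the mITT and PP analysis sets unless otherwise specified".

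The protocol (20.4.6) says: "Effectiveness endpoints and procedural data will be analyzed in FAS and PP analysis sets for respectively Wave I and Wave II". The sentence before it has the same construction: "Additional safety endpoints will be analyzed in Roll-in, Safety and mITT analysis sets for respectively Wave I and Wave II". Protocol 8.2.3 lists among the procedural endpoints "Use of paralytics and anesthesia", with no restriction to Wave I, and 14.2.3.1 includes paralytics in the electronic data capture.

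The Wave I SAP (7.6.1) includes paralytics in its list and says: "These analyses will be conducted separately in the FAS and PP analysis sets".

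**The concern.** The protocol appears to ask for a broad set and a restricted set for procedural data. The Wave II SAP keeps only the restricted one. Membership of PP is decided partly by what happens during the procedure: whether energy was delivered, where it was delivered, and whether entrance block was checked after the drug challenge. A table of procedure times restricted in that way describes completed, protocol-conforming procedures rather than all procedures in which the device was inserted.

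The unnamed item matters because it relates to the device's rationale. Protocol 6.1 puts forward the belief that a biphasic waveform will reduce muscle contraction and so permit procedures without paralytic agents. The share of procedures that used paralytics is the trial's direct descriptive evidence on that point.

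Procedural data are among the results to be shown at the early success interim (Wave II SAP 7.6), and early success can lead to a CE Mark filing (protocol summary). Protocol 6.4.3 also expects shorter procedures from this catheter.

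**Working it through.** The plan states no figure on this point, so the check is a comparison of texts.

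**1. Analysis sets by endpoint family, Wave II main phase**

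| Endpoint family | Protocol | Wave II SAP |
|---|---|---|
| Primary safety | mITT (20.4.4) | mITT; FAS as sensitivity (7.4.1) |
| Primary effectiveness | PP (20.4.4); mITT and PP for the descriptive summary after early success (20.4.4.3) | PP; mITT as sensitivity (7.4.2) |
| Secondary | mITT (20.4.5) | mITT and PP (7.5) |
| Additional safety | Roll-in, Safety and mITT (20.4.6) | FAS and mITT (7.6.2) |
| Additional effectiveness | FAS and PP (20.4.6, ambiguous) | mITT and PP (7.6.3) |
| Procedural data | FAS and PP (20.4.6, ambiguous) | PP only (7.6.1) |

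Procedural data are the only family with a single set. No other main-phase table recovers the subjects left out.

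**2. How to read protocol 20.4.6**

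The word *respectively* permits a one-to-one reading: FAS for Wave I, PP for Wave II. On that reading 7.6.1 complies. Against it, the preceding sentence uses the same construction with three sets and two waves, where one-to-one pairing is impossible. The Wave I SAP also uses both FAS and PP for procedural data, not FAS alone. Both sets in each wave is therefore the better reading, though not the only possible one.

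**3. Who is outside PP**

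From the definitions in Wave II SAP 5.1:

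- FAS minus mITT = subjects found ineligible.
- FAS minus PP = those subjects, plus subjects with no PFA delivered, subjects not treated for the study arrhythmia, IRE use outside the PV region, entrance block not checked after challenge, and any other major deviation.
- The SAP's PP definition does not list use of a non-study catheter for PVI as an exclusion, and it keeps eligible subjects treated with commercial catheters for non-PV triggers. The protocol's PP definition (20.3.2) excludes both groups.

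A subject with no PFA delivered because of a system malfunction counts as an effectiveness failure (7.4.2). That subject's procedure, fluoroscopy and dwell times appear nowhere.

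**4. Item lists**

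Protocol 8.2.3 and Wave II SAP 7.6.1 run in the same order from total procedure time to ablation settings. They differ only in the last item: paralytics and anesthesia in the protocol, anesthesia alone in the SAP.

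**5. Size**

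Let q be the share of FAS subjects outside PP, and d the mean duration outside PP minus the mean duration in PP. Then

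mean(FAS) = (1 − q) × mean(PP) + q × (mean(PP) + d), so mean(PP) − mean(FAS) = −q × d.

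The documents give neither q nor d. As pure assumptions to show scale, take q from 0.05 to 0.10 and d of 60 minutes in either direction. Then q × 60 = 0.05 × 60 = 3 minutes up to 0.10 × 60 = 6 minutes. PP would understate the mean by that much if the excluded procedures are longer, and overstate it by as much if they are shorter.

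**The case against.** The strongest reply is that this is loose protocol wording and not an SAP error. Protocol 20.4.6 can be read literally in the SAP's favour, and the same paragraph names a Safety set that section 20.3 does not define. This stands in part: a clear breach of the protocol cannot be shown, and clarifying the protocol is a legitimate remedy.

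Four stronger readings are tempting, and the documents do not support them.

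- *The Wave II SAP breaks the protocol by never analysing effectiveness in the FAS.* It is true that no main-phase effectiveness analysis uses the FAS. But the protocol assigns primary effectiveness to PP and secondary endpoints to mITT. Only the additional endpoints and procedural data are open to question.
- *The hardest cases drop out of the effectiveness summaries.* They do not. The mITT set differs from the FAS only by ineligible subjects, and nothing suggests that these are procedurally difficult.
- *Procedure time will be understated.* The direction is unknown. Cases that needed touch-up with another catheter, plausibly among the long ones, are not excluded from the SAP's PP set. An abandoned case with no energy delivered may be short, and a missed entrance-block check is an omitted step.
- *Wave I and Wave II tables cannot be compared.* They can, PP to PP. The Wave I SAP's change history says that its PP definition was aligned with Wave II.

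On paralytics, the SAP list is introduced by *such as*, and 7.6 promises descriptive statistics on all additional endpoints. The item is therefore unnamed rather than expressly dropped. That softens the point, but 7.6 ties the promise to the sets specified below it, and none is specified for this item by name.

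Finally, PFA application time, number of applications and settings are zero or undefined when no energy was delivered, so PP is a reasonable denominator for those items. That is right, and the fix allows for it.

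**Conclusion.** The point holds as a minor one. Wave II SAP 7.6.1 uses PP alone for procedural data, against the better reading of protocol 20.4.6, and does not name paralytic use, which is a protocol endpoint and is collected. Main-phase subjects with catheter insertion who fall outside PP contribute to no procedural summary. The size and direction of the effect cannot be derived from the documents; the 3 to 6 minutes in the working are a scale under assumed inputs, not an estimate. For the additional effectiveness endpoints, replacing the FAS with mITT changes the population only by ineligible subjects and is of little consequence.

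The conclusion rests on reading 20.4.6 as both sets in each wave. On the literal reading the PP-only choice complies. It would still leave procedural data as the only family with one set, and the paralytics point does not depend on that reading. All these endpoints are descriptive, and no primary, secondary or safety conclusion turns on them.

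**What to change.** In Wave II SAP 7.6.1:

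- Summarise procedural data in the FAS beside PP.
- Use all FAS subjects with data as the denominator for procedure, mapping, fluoroscopy and dwell times and for paralytics and anesthesia. Summarise PFA application time, number of applications and ablation settings among subjects with energy delivered.
- Name paralytic use in the list.
- Show the number of FAS subjects outside PP by reason, so that a reader can judge any difference between the two columns.

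For Wave II SAP 7.6.3, either add the FAS, or clarify protocol 20.4.6 and state why Wave II uses mITT and PP. In either case, reword 20.4.6 so that the sets for each wave are listed separately.

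The cost is a few descriptive columns and a denominator note. Paralytic use is already in the planned data capture, so no new data are needed, and the hypothesis tests and type I error are unaffected.
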